2.2.2. Objectives

Objective 1

We will identify cohorts of emergency admissions to NHS hospitals between 1 April 2009 and 30 June 2020 (subject to data availability). Our preparatory research has considered five of the 50 diagnostic categories from the precedent study¹. These five acute conditions were chosen because: they are common reasons for emergency admissions in the NHS with clearly defined non-operative strategies, and there is clinical uncertainty as to whether emergency surgery is effective and cost-effective compared to alternative strategies (see Table 1).

The final definitions of inclusion criteria for each population, interventions, and comparators will be informed by a clinical panel that will be convened during the initial phase of the study (months 0-6). The clinical panel will have three purposes: first to finalise the choice of target population according to ICD-10 diagnostic codes; second to define the list of 'intervention' and 'comparator' strategies from Office of Population Censuses and Surveys (OPCS) procedure codes; and third to check the plausibility of the main IV assumptions (see IV section below). As well as obtaining the most plausible definitions and assumptions for the main analysis, we will also obtain alternative but reasonable definitions to inform accompanying sensitivity analyses (see analysis section below).

Members of the clinical panel are required to have: involvement in the clinical management or commissioning of acute services for patients with the conditions listed above, and an understanding of the common operative and non-operative alternatives for these patients. The members of the clinical panel will be drawn from clinicians working within EGS including surgeons and nurses, but also other specialities including geriatric medicine, gastroenterology, radiology, acute and emergency medicine. The panel will participate in a face-to-face workshop (Design Workshop 1) to finalise the key definitions and assumptions that will be used in the study. We will also convene a Patient and Public design workshop (Design Workshop 2) that will complement the clinical panel by helping contextualise the choice of populations, interventions and comparators, and advise on the

selection of outcomes from HES and literature-based HRQoL estimates (see also objective 2, and PPI section for full details).

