The main potential issues are missing values for case mix variables and failure to record diagnoses, procedures or outcomes. Missing or unreported ethnicity data in eligible admissions (c10%), and deprivation (c1%) will be minimised by using ethnicity and deprivation data from patients' other linked episodes. HES data for age and sex are almost complete. We will recognise the potential impact of improvements in the coding of diagnoses in HES between 2008-2020 by including a covariate for financial year in the analysis models. We will examine the use of diagnosis/procedure codes over time periods to identify other potential issues that need to be considered in defining PICO criteria, for example expanding eligibility to include secondary as well as primary diagnoses. For any missing covariate data, we will make plain any assumptions that we do make, drawing on previous work from ourselves and our collaborators. For example, for baseline covariates with missing values we will examine whether this pattern of missingness differed across the intervention and comparator groups. We will use the approach recommended by Rosenbaum (2010) to making minimal, but transparent assumptions about the missing data while balancing patterns of missingness across intervention and control groups³⁰.

Instrumental variable

Our proposed IV design follows research in pharmaco-epidemiology²⁶ that uses provider preference as an instrument for treatment receipt. In this study, the IV will be the TTO, defined for each acute condition, as the proportion of emergency admissions during which an eligible surgical procedure is undertaken. Hospitals and surgeons will be identified from the HES provider/site of treatment codes, and the consultant/specialty codes as in precedent research by the applicants^{1,30}. In the primary analysis, TTO will be defined at the hospital-level, to recognise that in the NHS, multidisciplinary team input informs the decision to operate. We will also report sensitivity analyses with TTO defined at the trust-level, as in the pilot data, and at the consultant-level, for comparison with the precedent study¹. We will calculate TTO by financial year (2008-09 to partial 2020-21) using HES records for all relevant patients.

Sample size

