In the HES pilot data, we found that the trust-level TTO was strongly associated with receipt of emergency surgery; for each condition the F-statistics exceeded the critical value of 10, and therefore assumption i) was satisfied (see Table 1)³¹. We will repeat these tests of instrument strength for the full HES data for each level of the TTO. For assumption ii) we found that the trust-level TTO balanced the observed covariates, and we will explore this further in the full HES data^{32,33}. Although we cannot assess empirically whether TTO is independent of unmeasured confounders, in the emergency setting this assumption is likely to be justified for hospitals, since the vast majority of patients will attend their local hospital without consideration of the hospital-level TTO. This assumption will be bolstered by the exclusion of patients referred to tertiary referral centres for whom this assumption is less plausible. These patients can be identified from HES data on admission source, and distance to provider. For assumption iii) it seems unlikely that after adjusting for the volume of EGS and the outcomes of previous admissions, that the TTO would have a direct effect on the outcomes. For example, it is unlikely that just because a surgical team prefers to operate, that the patients' outcome would be better (or worse) unless that patient actually underwent an operation. We will use falsification tests to probe the plausibility of assumptions (ii) and (iii). Specifically, we will identify subgroups where all patients receive emergency surgery, and test whether the TTO has an effect on outcomes in these subgroups^{34,35}.

Most IV applications also assume that there are 'no defiers' – patients treated contrary to the physicians' preference^{33,36}. Here, this implies that there are no patients who receive surgery simply because they present in a high TTO hospital and vice versa. Following the approach of Swanson et al. (2015)³⁷ for checking the assumption of 'no defiers', we will survey the clinical panel about their preferences and choice of strategy for a set of hypothetical patients with the above acute conditions using vignette patient profiles. This will allow us to assess the magnitude and direction of any bias due to the presence of no defiers.

Estimation and sensitivity analyses

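### The vignette survey gives only indirect evidence on monotonicity for the hospital-level instrument and cannot supply the size and direction of bias that the protocol promises from it

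*Protocol*

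**What the plan says.** All references are to Protocol section 2.2.2, Objective 1, unless stated.

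- **Level of the instrument** (Instrumental variable): the protocol states that "TTO will be defined at the hospital-level, to recognise that in the NHS, multidisciplinary team input informs the decision to operate". Trust-level TTO is a sensitivity analysis, and so is TTO "at the consultant-level, for comparison with the precedent study".
- **Check of no defiers** (Checking IV assumptions): "we will survey the clinical panel about their preferences and choice of strategy for a set of hypothetical patients", using vignette profiles and following a cited published approach.
- **What the check is to deliver** (same place): "This will allow us to assess the magnitude and direction of any bias due to the presence of no defiers". Presumably the presence of defiers is meant.
- **Panel:** members need "involvement in the clinical management or commissioning of acute services for patients with the conditions listed above". The next sentence draws them from clinicians in emergency general surgery and other clinical specialities.
- **Related work:** instrument-strength tests are repeated at each TTO level. Falsification tests address independence and exclusion. Nonparametric bounds and a sensitivity analysis for an unobserved confounder are planned under Estimation and sensitivity analyses.

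**The concern.** For a hospital-level instrument, monotonicity is a statement about hospitals: no patient who would be operated on in a lower-TTO hospital would go without surgery in a higher-TTO one. The survey records what individuals would choose. The protocol gives no step that links a member's answer to any hospital's TTO or combines answers into a team decision, although it is the team decision that justifies the hospital level.

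The second difficulty is the promised product. The bias from defiers depends on how the effect of surgery differs between compliers and defiers. A survey of preferred strategies holds no information on outcomes.

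The stake is largest in Objective 3, which reports local-IV estimates by age, comorbidity and admission route. If high-TTO hospitals operated more on fit patients but less on frail ones, the estimates for the frail would be affected, and the survey might not show it.

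**Working it through.** The protocol gives no figure for the defier share or its bias, so there is none to reproduce. Four checks follow.

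**1. What the bias depends on.** Let pC and pD be the shares of compliers and defiers for a contrast of high with low TTO, and τC and τD the effects of surgery in each. The IV estimand is (pC·τC − pD·τD)/(pC − pD). Subtracting τC gives

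bias = pD/(pC − pD) × (τC − τD).

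The denominator pC − pD is the first-stage contrast. As a proxy I take the trust-level interquartile range in Table 1. The 2% defier share and the effect differences are assumptions.

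| Condition | Contrast (points) | Bias, difference 0 | Difference 5 points | Difference 10 points |
|---|---|---|---|---|
| Diverticulitis | 10.9 − 6.6 = 4.3 | 0 | 2.3 | 4.7 |
| Appendicitis | 92.8 − 84.9 = 7.9 | 0 | 1.3 | 2.5 |
| Intestinal obstruction | 34.3 − 25.5 = 8.8 | 0 | 1.1 | 2.3 |
| Cholecystitis | 25.0 − 11.2 = 13.8 | 0 | 0.7 | 1.4 |
| Hernia | 58.7 − 39.4 = 19.3 | 0 | 0.5 | 1.0 |

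For example, diverticulitis: 0.02/0.043 × 10 = 4.7. With 5% defiers it is 0.05/0.043 × 10 = 11.6. The sign follows τC − τD. Even an exact defier share would therefore leave both size and direction open.

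**2. Individual answers against hospital behaviour.** An illustrative simulation used 60 hospitals of 8 clinicians and 20,000 patients, with clinician preferences always drawn from the same distribution. Top and bottom TTO quartiles were compared. The defier share between individual clinicians stayed at 0.2% to 0.6%. Between hospitals it was 0.3% when the decision was the team average and 0.5% when one clinician decided. It rose to 4.3% or 11.3% when factors specific to the patient and hospital (SD 0.5 or 1.0, against a patient-need SD of 1) were added. All settings are assumed. The same kind of survey result can go with quite different hospital-level behaviour.

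**3. Whether other planned work fills the gap.** F-statistics show average strength, not whether the effect of TTO reverses in some patients. The falsification tests are aimed at other assumptions. The bounds do not show which patients violate monotonicity.

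**4. A direct check, and a trap in it.** HES holds the subgroup variables, so surgery can be regressed on hospital TTO within subgroups. The protocol computes TTO by financial year from all relevant patients, so each patient's own operation enters the regressor. If the true slope in a small subgroup is zero, the fitted slope is about

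q/(σ² + q), with q = p(1 − p)/m,

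where m is patients per hospital-year, p the median TTO, and σ = IQR/1.349. If the observed spread in Table 1 already contains the sampling noise, the ratio is q/σ². With Table 1 cohorts, 9 years and an assumed 150 to 200 hospitals:

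- Diverticulitis: m = 224,000/(9 × 150) = 166 to 224,000/(9 × 200) = 124; q = 0.0819/m = 0.00049 to 0.00066; σ² = 0.00102. Slope 0.33 to 0.65.
- Hernia: m = 52 to 39; q = 0.2489/m = 0.0048 to 0.0064; σ² = 0.0205. Slope 0.19 to 0.31.
- Obstruction: m = 174 to 131; q = 0.2096/m = 0.0012 to 0.0016; σ² = 0.00425. Slope 0.22 to 0.38.

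A reversal could thus be hidden. I simulated these three conditions with a 10% subgroup and a true slope of zero. Computing TTO from patients outside the subgroup brought the mean fitted slope to within 0.003 of zero.

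Precision is not the obstacle. With independent patients, the standard error √(p(1 − p))/(σ√(0.1n)) in a 10% subgroup is 0.018 (cholecystitis) to 0.060 (diverticulitis). It is at most 0.18 if clustering triples it. This uses trust-level spread as if it were the true hospital spread.

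**The case against.** The strongest reply has four parts.

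- **The survey follows a published approach, and its details may sit in a later analysis plan.** The mechanics can be left there. But the protocol itself states what the survey will deliver, and answers about preference do not contain that quantity unless effects in defiers are brought in from elsewhere.
- **The survey is informative.** This stands. If clinicians order patients differently, that bears on monotonicity, most directly for the consultant-level sensitivity analysis. A reader might infer that the survey is worthless for the primary analysis. The documents do not support that; it is indirect evidence.
- **The panel is suitable.** This stands too. A reader might infer from the eligibility wording, "involvement in the clinical management or commissioning of acute services", that commissioners or people with no part in the decision would distort the survey. The protocol draws members from clinicians, and a mixed panel fits its reason for the hospital level, that "multidisciplinary team input informs the decision to operate". What is missing is a step from individual answers to a hospital decision.
- **Other robustness work exists.** Bounds and a confounder sensitivity analysis are planned, so the survey is not the only safeguard on the IV assumptions. It is the only check tied specifically to no defiers.

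It is also fair to say that the same paragraph has a more basic fault. Its gloss on no defiers, that nobody is operated on merely because the hospital's TTO is high, describes an absence of compliers. That should be corrected first, but doing so would not resolve the present point.

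**Conclusion.** The point holds in a limited form. The survey's unit is the individual and the primary instrument's unit is the hospital, so the survey is indirect, qualitative evidence on the assumption the main analysis needs. The statement that it will yield the magnitude and direction of bias is not supportable.

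The illustration for diverticulitis, 0 to 4.7 points at 2% defiers, shows that the unmeasured effect difference alone can move the bias from nothing to nearly the 5% difference named under Sample size. It rests on assumed defier shares and effect differences, and on trust-level spread standing in for hospital-level spread.

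A reader might go further and infer that monotonicity fails, or that the estimates are biased. Nothing in the documents shows either. Nor do they support saying that a reversal would be plain in every condition from a simple subgroup regression: with TTO calculated as the protocol now describes, the slope is pushed upward.

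**What to change.** 1. Withdraw the claim that the survey gives the magnitude and direction of bias. Alternatively, replace it with the formula above and a stated range for the hospital-level defier share and the effect difference.
2. For each condition, regress surgery on hospital TTO within each pre-specified subgroup (age, comorbidity, deprivation, admission route, diagnostic subcategory). Compute TTO from patients outside that subgroup and cluster standard errors by hospital.
3. Report a non-positive slope as evidence against monotonicity, next to that subgroup's effect estimate.
4. Keep the vignettes, with the multidisciplinary panel, as supporting evidence.

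The cost is a change of wording and a few regressions on data the study will hold. The limit is that a positive slope in every subgroup is a necessary condition only. Defiers could still exist within a subgroup, and the report should say so.

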Exclusion criteria for defining the *index admission* will include: age less than 18, a previous emergency admission for the condition within the year prior to the index admission, referrals from tertiary referral centres (see IV assumptions below), and any additional exclusion criteria deemed appropriate by the clinical panel, for example minimum surgical volume thresholds for a particular hospital.

Table 1: Exemplar acute conditions, interventions and comparator strategies, and trust-level tendency to operate (TTO), from pilot HES data (2014-5)

Acute condition ¹	Population ² (estimated cohort 09-18)	Intervention ³	Comparator ³	NHS Trust TTO ⁴ median (IQR)	F statistic ⁵
Appendicitis	333,000	Appendectomy	Supportive care; Antibiotic treatment	89.3% (84.9%, 92.8%)	114
Cholecystitis	422,000	Cholecystectomy	Delayed cholecystectomy	17.3% (11.2%, 25.0%)	65
Diverticulitis	224,000	Resection; Colectomy; Laparoscopic lavage	Antibiotic therapy; intravenous fluid therapy Percutaneous	9.0% (6.6%, 10.9%)	678

			drainage of abscess		
Acute symptomatic hernia ⁶	70,000	Repair of hernia	Watchful waiting; Delayed repair of hernia	46.7% (39.4%, 58.7%)	148
Intestinal obstruction (small or large bowel)	235,000	Adhesiolysis; Colonic stenting; Bowel resection	Watchful waiting with intravenous fluid	29.9% (25.5%, 34.3%)	931

¹Acute condition refers to pathology and ensuing complications. The clinical panel will define specific complications related to pathology for the final inclusion criteria ²Population defined by ICD-10 codes. ³Intervention and elective surgery comparators are defined by OPCS codes. ⁴Percentage of the eligible population with an intervention within index HES episode. ⁵From Cragg-Donald weak identification test. ⁶Includes inguinal hernia, femoral and incisional.

Intervention

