We will use the generalized effect ratio³⁸, that provides the same point estimates as two-stage least squares, but also correct confidence intervals³⁹. For survival outcomes, we will apply IV methods for Cox survival models^{40,41}.

We will undertake three extensive sets of sensitivity analyses. First, we will draw from the views of the clinical panel to test whether the conclusions are robust to alternative but plausible selection criteria for the subpopulations, interventions and comparators of interest (see earlier section). Second, we will assess the robustness of the major IV assumptions by reporting nonparametric bounds for the IV estimate⁴², and investigating the extent to which results are robust to the association of an unobserved confounder with both the IV and the outcome^{25,43}. We will investigate whether our results are robust to alternative statistical models by estimating results based on logistic regression models using the plug-in principle for estimation⁴⁴.

Output

We will report the relative effectiveness of emergency surgery versus comparator strategies for each of the five acute conditions, for patients presenting as emergency hospital admissions to NHS hospitals in England.

Objective 2

Design

The CEA will take a hospital and personal social services perspective (PSS)⁴⁵. In the base case, the study will report results over a one-year time horizon and incorporate patient-level resource use (HES) and mortality data (ONS), and estimates from the literature for HRQoL⁴⁶, community care costs⁴⁶, and unit costs^{47,48}.

Resource use and unit costs

The study will measure resource use items that are the major drivers of relative cost and cost-effectiveness for patients with relevant acute conditions^{49,50}. These resource use categories are: the receipt of operative and other procedures, the duration of hospital stay for the index admission, subsequent readmissions or re-interventions, and transfer to continuing care, in particular, care homes.

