We will estimate the relative costs and cost-effectiveness of emergency surgery (operative) versus comparator strategies for each acute condition according to broad ICD-10 diagnostic categories. We will report incremental costs per life year and per QALY gained. The main cost-effectiveness metric will be the incremental net monetary benefit, which will be calculated by valuing QALYs by the NICE recommended thresholds of £20,000 and £30,000 per QALY, and then subtracting the incremental cost⁴⁵. In the base case analysis, we will use 3 stage least-squares (3SLS) regression approaches that we have developed for IV designs that allow for the correlation between the costs and QALYs while estimating cost-effectiveness⁵⁹.

We will undertake extensive sensitivity analyses to test whether conclusions are robust to key assumptions. We will consider the impact of taking a hospital versus PSS perspective, to using different sources for the HRQoL and unit cost data, to alternative assumptions about the distribution of the cost data (e.g. gamma or log normal distribution) and to taking a longer time horizon (lifetime vs one year). To estimate lifetime cost-effectiveness, we will access use all HES-ONS linked mortality and resource use data subsequent to the index admission (up to March 2018), which will provide up to 10 years follow-up data. The long-term modelling will extrapolate from these observed data by fitting alternative parametric survival curves (e.g. Weibull, exponential, lognormal, log logistic and Gompertz). We will choose the extrapolation approach that gives the most plausible predictions of long-term survival⁶⁰.

Outputs

We will report the relative cost-effectiveness of emergency surgery versus comparator strategies for these five common acute conditions.

Objective 3

Design

We will estimate the relative effectiveness and cost-effectiveness of emergency surgery, according to patient subgroup. We will recognise that effectiveness and cost-effectiveness may differ according to observed and unobserved patient- and service-level characteristics. We will predict counterfactual outcomes following both emergency surgery (operative care) and the comparator for each patient using the local-IV (LIV) approach developed by Basu^{2,61,62}. We will generate individual-level

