The research will provide recommendations to commissioners and providers of surgical services on those services where disinvestment is warranted, those where additional investment is required, and those where additional evidence, for example from new RCTs, would be of greatest value.

The research findings will be presented at high profile national and international clinical conferences (surgical, perioperative). While the study has used HES data from England, we will ensure that both the empirical and methodological insights have wide relevance. We will work with our international network of surgeons, and with our international advisory panel (see below), to consider carefully the direct implications of the findings to other countries. The methods will be discussed at academic meetings, in particular the Health Services Research network, and Health Economist study group meetings in the UK, the European Causal inference network, and the American Health economists study group meeting (USA).

The design and translation workshops will draw on the views of patient representatives, and will consider the translation of the findings into accessible and informative summaries appropriate to the audiences of interest, and effective modes of dissemination via special interest groups (see below for further details). The findings will be presented to select groups of professional stakeholders (for example NICE guidelines committees, NHS England), commissioners and managers of surgical services and those setting future research priorities. We will work closely with [name] and colleagues at the University of Pennsylvania to ensure that this work is disseminated throughout

international surgical networks, in particular through presentations at the American College of Surgeons Clinical Congress. This congress will provide an excellent opportunity to translate the implications of the findings, and the wider application of the methods to key surgical opinion leaders.

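### The Objective 1 and 2 outputs and the person-level effects are worded for all patients with each condition, but the TTO design identifies effects only for patients whose treatment depends on TTO

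*Protocol*

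**What the plan says.** All references are to the protocol; unless stated otherwise they are to section 2.2.2.

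- **Objective 1, estimation and output.** The main estimator is the generalized effect ratio, which the protocol says has the two-stage least-squares point estimate. The output is the relative effectiveness of surgery "for each of the five acute conditions, for patients presenting as emergency hospital admissions to NHS hospitals in England".
- **Objective 2, analysis and outputs.** Costs and QALYs are estimated by three-stage least squares. The output is cost-effectiveness for the five conditions.
- **Objective 3, design and analysis.** "We will predict counterfactual outcomes following both emergency surgery (operative care) and the comparator for each patient", using a local instrumental variable (LIV) approach. Effects are expected to be heterogeneous and are said to be learned from marginal patients, for whom a small change in TTO decides whether surgery takes place. Person-level effects are then produced for every patient and averaged by condition and subgroup.
- **Instrument.** "In the primary analysis, TTO will be defined at the hospital-level", calculated by financial year. Table 1 reports TTO by trust.
- **Checking IV assumptions.** Falsification tests will use subgroups in which every patient has surgery. The no-defiers assumption is explained as meaning that nobody is operated on merely through arriving at a high-TTO hospital.
- **Section 4.** Recommendations will cover "those services where disinvestment is warranted, those where additional investment is required", and also areas where more evidence would be most valuable.

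**The concern.** With a preference-based instrument and effects that vary between patients, a two-stage least-squares type estimate is a weighted average over patients who would be operated on at a higher-TTO hospital but not at a lower-TTO one. The data hold no contrast for patients who would be operated on everywhere, or nowhere. Objective 3 recognises this by building its argument on marginal patients. The Objective 1 and 2 outputs do not, and Objective 3 itself goes on to assign an effect to everyone.

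At stake is who the results are about. An effect learned at the margin could be read as the effect for the whole condition and carried into the investment and disinvestment advice of section 4. Person-level and subgroup effects outside the supported range of propensity would be reported in the same form as those inside it, although they rest on the form of the propensity and outcome models.

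**Working it through.** **1. The plan's own figure.** The protocol gives no share of patients whose treatment depends on TTO. The nearest stated figure is pilot power for a 10% risk difference: 57% for diverticulitis, at least 99% for the others. The event rate is not given, so this cannot be reproduced from stated inputs. Assume nine cohort years, half of trusts, a first-stage slope of 1, no clustering and a two-sided 5% level:

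- N = 224,000 / 9 / 2 = 12,444; SD of TTO = 4.3 / 1.349 = 3.19 points.
- With an assumed event rate of 2.85%, SE = √(0.0285 × 0.9715 / 12,444) / 0.0319 = 0.047, and power = Φ(0.10 / SE − 1.96) = 57%. The other four conditions then reach at least 99.4%.
- At event rates of 2% and 5%, diverticulitis power is 72% and 37%.

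The stated pattern therefore fits an IV calculation in which narrow TTO variation limits the information.

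**2. Share whose treatment changes with TTO.** Under monotonicity, and with comparable patients across trusts, moving from a trust with TTO = a to one with TTO = b changes treatment for a share b − a. A share a is operated on at both, and 1 − b at neither. The inputs are the Table 1 quartiles. For the 5th to 95th percentile range a normal spread across trusts is assumed: width = 3.29 × IQR / 1.349.

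| Condition | Quartiles a, b (%) | b − a | Operated at neither (1 − b) | 5th–95th width |
|---|---|---|---|---|
| Appendicitis | 84.9, 92.8 | 7.9 | 7.2 | 19.3 |
| Cholecystitis | 11.2, 25.0 | 13.8 | 75.0 | 33.7 |
| Diverticulitis | 6.6, 10.9 | 4.3 | 89.1 | 10.5 |
| Hernia | 39.4, 58.7 | 19.3 | 41.3 | 47.1 |
| Obstruction | 25.5, 34.3 | 8.8 | 65.7 | 21.5 |

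Weighted by the Table 1 cohorts (1,284,000 in total), the quartile contrast is 10.0% and the 5th–95th contrast 24.4%.

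**3. Sensitivity of these shares.**

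- 1st to 99th percentile: 27.2, 47.6, 14.8, 66.6 and 30.4 points in table order. Normality fails here for two conditions: 17.3 − 47.6/2 is below 0 and 89.3 + 27.2/2 is above 100, so those two widths are too large.
- Hernia quartiles are lopsided (7.3 points below the median, 12.0 above), so normality is only rough there too.
- Removing binomial noise, with an assumed 50 to 80 pilot trusts, lowers the 5th–95th widths to about 18, 33, 7–9, 41–43 and 18–19 points.

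**4. What the data say without a model.** For a binary outcome, worst-case bounds on the all-patient effect have width 1 − (b − a). That is 80.7 to 95.7 points over the quartiles and 52.9 to 89.5 points over the 5th–95th range. Objective 3 takes a 10% difference in one-year mortality as the benefit of interest.

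**5. Person-level effects.** The propensity model uses covariates and TTO together, so pooled support is wider than the TTO range. For one covariate profile, however, only TTO moves propensity. Borrowing from other profiles relies on the propensity and outcome models. The protocol's own falsification subgroups, in which everyone is operated on, are profiles where TTO cannot identify an effect of surgery.

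**6. No defiers.** The patients ruled out by that explanation, those who have surgery because their hospital's TTO is high, are the marginal patients on whom Objective 3 relies. The two descriptions cannot both stand.

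**The case against.** The strongest case against is that this is a matter of wording and detail. The Objective 1 output is a one-line summary and does not define an average over every patient. The protocol names marginal patients, plans nonparametric bounds and alternative LIV forms, and cites for its three-stage approach a methods paper on complier average causal effects. Section 4 leaves room for areas needing more evidence, and section 5 says analysis plans will be published separately. Table 1 is exemplar pilot data at trust level, from half of trusts in one year, not the primary instrument.

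Much of this limits the size of the point. A reader might infer from Table 1 that most patients are never marginal, that the share affected is small for every condition, or that person-level effects come only from the assumed probit shape. The protocol does not support those readings. An interquartile range describes the middle half of trusts and cannot show that any type of patient is never marginal. Hernia (19.3 to about 47 points) and cholecystitis (13.8 to about 34) are not small. LIV support also draws on covariates. Nor is the promise about all emergency admissions: it concerns eligible adults with one of five conditions.

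The mismatch itself remains. A citation title does not tell a reader whom the output describes. The bounds are planned as a check on IV assumptions and are not tied to patients outside support, and alternative functional forms compare one extrapolation with another. A support check could sit in an analysis plan, but the population and per-patient claims are made in the protocol.

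**Conclusion.** The point holds as a mismatch between the population claimed and the population identified. Given the heterogeneity that the protocol assumes, and monotonicity, the Objective 1 and 2 estimates apply to patients whose treatment depends on TTO. On pilot trust-level data the quartile contrast is 4.3 to 19.3 points, and roughly 10 to 47 points over an assumed-normal 5th to 95th range. For appendicitis, diverticulitis and obstruction, treatment is unaffected for most patients under every range tried. The hospital-by-year range is unreported and may be wider, so these figures illustrate the issue and do not measure the final share. How many patients fall outside propensity support cannot be derived from the protocol. The design is not invalidated: the plan as written would over-generalise its results, and this should be corrected before they are interpreted.

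**What to change.** - **Objectives 1 and 2, outputs:** state that the estimates apply to patients whose treatment depends on hospital TTO. Report the observed hospital-level TTO range and the implied share for each condition.
- **Objective 3, design and analysis:** check propensity support by covariate profile and report the number of patients outside it. Label person-level and subgroup effects outside support as model-based extrapolation, and show condition and subgroup averages with and without those patients. Full-population averages need not be moved to sensitivity analysis.
- **Section 4:** word the recommendations to match the groups the data support.
- **Checking IV assumptions:** reconcile the description of no defiers with the marginal patients of Objective 3.

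The cost is some rewording and a support check on models already planned. The downside is narrower claims, with some subgroups flagged as weakly supported.
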